Prospective, Multi-Center Evaluation of the Efficacy of Migraine Surgery

Statistical Analysis Plan

IRB Approval #:2015H0024

NCT02351544

Document Date Version: February 16, 2014

Principal Investigator: [name], FACS (The Ohio State University)

Outcomes

**Outcomes modeled were: MHI, MIDAS A, MIDAS B, MIDAS Total, MSQ Sum and MWPLQ7 Total

Data Analysis

Descriptive statistics, such as frequency and percents, were displayed for sex (male or female), treatment (Botox or Surgery) and site (OSU or MGH). Descriptive statistics, such as mean, standard deviation, median, lower quartile and upper quartile, were reported for age and the patient reported outcomes with the respect to their migraine for each time point (baseline, 1 year, 2 years and 2.5 years).

Each of six outcomes were highly skewed and therefore natural logarithm was applied to each one before it was modeled. A constant of 1 was added to outcome values before applying natural log function so as to include raw values of zeros.

Linear mixed models with a random effect for patient were used to evaluate the changes in each of six outcomes between two different treatments over time with inclusion of interaction between treatment and time. These models were used given to account for correlation between repeated measurements on the same patient and to account for missing data across time points. P-values for both the main and interaction effects of time and treatment were reported for each model and Tukey's post hoc method was used to adjust for pairwise comparisons. For the ease of interpretation, raw means and SDs are presented for each time point within specific treatment.

Analyses were performed using SAS v9.4 (SAS Institute; Cary, NC; www.sas.com). Statistical significance was defined as two-sided alpha<0.05.

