Since there are several endpoints in this study, the required sample size can be calculated in several ways:

-Using efficacy as an endpoint:

In Janis *et al*,⁶ patients undergoing botulinum toxin injections had an average improvement in their Migraine Headache Index of 87.5%. In comparison, patients undergoing surgery had an average improvement of 96.6%.

Assuming a standard deviation of 20%, an alpha error of 5%, and a power of 80%, the required sample size using this method is **30 patients in each group**.

-Using total cost of treatment as an endpoint:

Assuming an average injection volume of 75 Units of botulinum toxin every 3 months, and assuming a cost of \$12-15 per Unit, the estimated cost of a botulinum toxin A injection protocol over one year is \$3,600-\$4,500.

In comparison, the estimated cost of surgery (including facility fee, surgeon fee, preoperative testing and follow-up) is \$8,378.¹⁰

Therefore, in order to demonstrate a financial superiority of surgery versus botulinum toxin, the patients would need to be follow-up for 1.9 to 2.3 years. Assuming a study follow-up of 2.5 years, and average costs of botulinum and surgery of $$10,125 \pm $2,000$ and $$8,378 \pm $2,000$, respectively, and assuming an alpha error of 5%, a power of 80%, the required sample size using this method is **16 patients in each group**.

-Using treatment success by trigger site as an endpoint:

According to Larson *et al*,⁹ the success rates for surgery by trigger site were as follows: Frontal 83.3%, temporal 75.8%, and occipital 45.5%. In order to discern a difference between the outcomes for the two sites with the closest outcomes (frontal and temporal), and assuming a standard deviation of 10%, an alpha error of 5%, and a power of 80%, the required sample size using this method is **14 patients in each group**.

Looking at the three methods above, keeping the method yielding the highest required number of participants, and accounting for any participant drop-out, we will seek to enroll **50 patients in each group.**

c. Detailed study procedures

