and the Migraine-Specific Quality of Life questionnaire (MSQ). They will also be examined by a board-certified neurologist at 1 year postoperatively.

The Botox injections and the surgeries are being done as part of the routine clinical care for the patients enrolled in the study. The only procedures being done solely for research purposes are having the patients fill out the surveys and diaries.

d. Measurements

The measurements will include

- 1) Number of migraine headaches per 30 days
- 2) Cost of migraine-related medications, physician visits, ER visits
- 3) Cost of days of work lost due to migraine as calculated from the Migraine Work and Productivity Loss Questionnaire (MWPLQ)
- Score on the Migraine Disability Assessment Questionnaire (MIDAS) (0-21)
- 5) Scores on the emotional, restrictive and preventive portions of the Migraine-Specific Quality of Life questionnaire (MSQ)

The following comparisons will be made for the above measurements:

-Within Group A, compare all measurements before surgery to 1 year, 2 years and 2.5 years after surgery, using a t-test

-Within Group B, compare all measurements before start of injection protocol to 1 year, 2 years and 2.5 years after injection protocol, using a t-test

-Compare all measurements between Group A and Group B using a paired t-test analysis

e. Internal validity

The study avoids confounding by virtue of the matched-pair analysis. The study avoids recall bias by having the patients fill-out the questionnaires preoperatively and postoperatively, rather than having them retrospectively assess their improvement after surgery.

Blinding is very difficult in such a study. In order to avoid experimenter bias, all assessment will be made by the patients themselves, without influence by the experimenters.

The main threat to internal validity is the possible placebo effect inherent to migraine headache treatments. This may threaten the validity of the data on differences in clinical outcomes between the two groups. It will not threaten the validity of the data on financial cost

f. External validity

Because this is a multi-center trial that includes different patient populations treated by different clinicians, this study is generalizable to the general population of patients with migraines in the United States.

g. Data analysis

Group B will be selected by matching individual participants to members of Group A based on gender, age, migraine severity and migraine location.

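### Neither document names a primary outcome or contrast for Objective 1, and six outcomes are each tested at two-sided 0.05 with no control across them.

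*SAP*

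**What the plan says.** SAP, Outcomes: "Outcomes modeled were: MHI, MIDAS A, MIDAS B, MIDAS Total, MSQ Sum and MWPLQ7 Total". No order or priority is given.

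SAP, Data Analysis: each outcome has its own linear mixed model with treatment, time and their interaction. On what is reported: "P-values for both the main and interaction effects of time and treatment were reported for each model". On multiplicity: "Tukey's post hoc method was used to adjust for pairwise comparisons". On the threshold: "Statistical significance was defined as two-sided alpha<0.05". Nothing is said about error control across the six outcomes.

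Protocol III.b, Sample size: "Since there are several endpoints in this study, the required sample size can be calculated in several ways". Three bases follow (efficacy, cost, success by trigger site). The efficacy basis is the MHI and gives the largest of the three sample sizes, 30 per group, but the MHI is not called primary.

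Protocol III.d, Measurements: five groups of measurements are listed, and the MHI is not among them. The between-group plan is "Compare all measurements between Group A and Group B using a paired t-test analysis", at 1, 2 and 2.5 years, with no hierarchy. Section III.g repeats this plan.

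Protocol II, Objective 1: surgery is expected to give a larger and longer-lasting reduction than botulinum toxin. No outcome, visit or contrast is attached to that hypothesis.

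**The concern.** A per-test threshold of 0.05 describes the error of a conclusion only when one pre-named test carries it. Here six outcomes are candidates, and each model yields a treatment and an interaction p-value. Tukey's method works among the pairwise comparisons within a model and does nothing across the six models.

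Two things are at stake. A favourable result on any one outcome could be presented as support for Objective 1, at an error rate above the stated one. And if the outcomes disagree, no rule says how to read them. This matters more than usual because patients choose their own treatment, assess their own outcomes and are not blinded; Protocol III.e accepts that a placebo effect may distort the clinical comparison.

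**Working it through.** **Inputs.** Six outcomes (SAP, Outcomes). Two-sided 0.05 per test, hence 0.025 in the direction favouring surgery (SAP, Data Analysis). Three p-values per model, two of which involve treatment. The documents give no correlation between outcomes, so a range is assumed.

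**Step 1, the plan's own figure.** The 0.05 is a declared per-test threshold, not a derived quantity. It equals the overall error for a single test: 1 − 0.95¹ = 0.050.

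**Step 2, six independent tests, one per outcome.** The rule assumed is that any one significant outcome counts.
- Either direction: 1 − 0.95⁶ = 1 − 0.735 = 0.265, against 0.05.
- Favouring surgery: 1 − 0.975⁶ = 1 − 0.859 = 0.141, against 0.025.

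The second line treats each test as a single contrast with a direction.

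**Step 3, correlated tests.** All six outcomes come from the same patients and three carry the MIDAS name, so independence is unlikely. Six normal test statistics with a common correlation were simulated (400,000 draws; Monte Carlo standard error near a rate of 0.2 is √(0.2 × 0.8 / 400,000) = 0.0006).

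| Assumed correlation | Either direction | Favouring surgery |
|---|---|---|
| 0 | 0.265 | 0.141 |
| 0.3 | 0.241 | 0.122 |
| 0.5 | 0.207 | 0.103 |
| 0.7 | 0.164 | 0.082 |
| 0.9 | 0.108 | 0.054 |

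Even at 0.9 both rates are about twice nominal: 0.108 / 0.05 = 2.2 and 0.054 / 0.025 = 2.2.

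**Step 4, both treatment-related p-values per model.** This makes 6 × 2 = 12 tests. If independent: 1 − 0.95¹² = 0.460. With correlation 0.3, 0.5, 0.7 and 0.9 across outcomes, and the two tests within a model treated as independent: 0.425, 0.371, 0.301 and 0.205. This is approximate, since the interaction is handled as a single normal statistic. It shows that one test per outcome is not the worst case.

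**Step 5, after a fix.** One named outcome with one named contrast: 5% two-sided, 2.5% favouring surgery. For comparison, Bonferroni over all six would use 0.05 / 6 = 0.0083 each, giving 1 − (1 − 0.0083)⁶ = 0.049 under independence. For five secondary outcomes, Holm's first step is 0.05 / 5 = 0.01.

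**The case against.** The strongest objection is that the documents never say Objective 1 is met if any one outcome reaches 0.05. That rule is supplied for the calculation. This stands: what the documents show is an unspecified decision rule, and the percentages describe one natural way of filling the gap.

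A reader might infer that the chance of a false positive for surgery is 26% instead of 5%. The documents do not support that. The threshold is two-sided, so 26% counts errors in both directions; the figure favouring surgery is 14%, to be compared with 2.5%. Both values also need independence, which is implausible here.

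A reader might also count all 18 p-values (six models, three each) and arrive at 1 − 0.95¹⁸ = 60%. Six of those are time main effects, which average over the groups and cannot show one treatment better than the other. The cited improvements of 87.5% and 96.6% in Protocol III.b also make a null of no change over time hard to credit.

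It is fair to add that the groups are formed by preference and matching, so residual confounding also affects the chance of a wrong conclusion. A multiplicity calculation does not capture that.

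Finally, the SAP carries a 2014 date but is written in the past tense and reports that the outcomes were skewed, so data may already have been seen. A primary outcome chosen after that would not restore 5% control. This limits what the fix can achieve but does not remove the need for a stated hierarchy.

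**Conclusion.** The point holds in this form: there is no primary outcome or contrast for Objective 1 and no error control across six outcomes. Reading any single significant outcome as success, with one test per outcome, gives at most about 26% in either direction or 14% favouring surgery. Over assumed correlations of 0.3 to 0.9 the ranges are about 24% to 11% and 12% to 5%. Using both treatment-related p-values raises them.

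The absence of a hierarchy is certain from the text. The size is not, because it depends on a correlation and a decision rule that the documents do not give. No single figure should be quoted as the trial's error rate. The plan should be changed, but the defect is one of specification and needs no new data.

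**What to change.** 1. In the SAP, name the MHI as the single primary outcome, on the ground that the efficacy sample size in Protocol III.b rests on it. Add the MHI to the measurement list in Protocol III.d and define it there.
2. Test it with one treatment-by-time contrast: the between-group difference in change from baseline at one named visit. The 2.5-year visit is an example, as the last planned one; the documents give no visit priority, so the choice must be stated and justified.
3. State that the time and treatment main-effect p-values are not evidence for Objective 1. The first ignores treatment and the second averages in the baseline.
4. Make the other five outcomes secondary, either Holm-adjusted at a family level of 0.05 (first step 0.01) or labelled exploratory.
5. If the data had been examined before the hierarchy is set, date it, label it post hoc, justify it by the sample-size section and not by results, and report all six outcomes.

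The cost is an edit to the SAP and to the protocol's measurement list. The downside is a stricter threshold for the secondary outcomes if they are Holm-adjusted, or no confirmatory claim from them if they are exploratory.

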Similarly, surgical decompression of trigger sites has previously been shown to have superior clinical outcomes to medical management, through a randomized, blinded controlled-trial performed at Case Western Reserve in 2009.⁷ Patients either received actual decompression of the trigger sites, or sham surgery (exposure and visualization of the trigger sites, without decompression). At one-year follow-up, the group who underwent actual surgery demonstrated a statistically higher proportion with significant improvement in their migraines (83.7% vs. 57.7%, p=0.014), and with complete elimination of their migraines (57.1% vs. 3.8%, p<0.001). Several other reports have confirmed the good clinical outcomes of surgery demonstrated in this trial,^{6,8} and surgical decompression is now commonly performed by several surgeons around the United States.

Prognostic factors predicting the success of surgical decompression in migraine headache treatment include older age of migraine onset, visual symptoms/aura, and 4-site decompression. Factors predicting failure of surgery include excessive operative blood loss, and surgery on only one or two trigger sites.⁹

One criticism of the studies on migraine surgery has been that most of the results have originated from the same institution (Case Western Reserve), and from the same author (Guyuron). While several studies at other institutions have demonstrated positive outcomes of migraine surgery,⁶ these have only included a small number of patients.

In addition, the sham surgery randomized-controlled trial has been criticized for not clarifying any prior treatments that patients had undergone before migraine surgery, and for not showing how medication use patterns changed after surgery. Another criticism of that study was the fact that patients were examined by neurologists before the study but not after the study, and that surgery was performed on some patients with episodic migraines, who are known to not benefit from botulinum toxin. It is unclear what migraine types are most likely to benefit from surgical decompression.

Our goal is to perform a multi-center, prospective trial to demonstrate the effectiveness of migraine surgery, which would address the criticisms mentioned above. The main aim is to demonstrate that the positive results demonstrated by Guyuron *et al* are reproducible at other institutions and by other surgeons using similar techniques on different patient populations.

II. Objectives

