A neurologist will evaluate patients presenting for evaluation for treatment of migraine headaches, for confirmation of the diagnosis of migraine. The type of migraine that they suffer from will be recorded. If the diagnosis of migraine is confirmed, they will sign an informed consent form, and they will be asked to complete a daily headache diary, and keep track of their 1) daily use of medications for migraines, 2) physician visits for migraines, 3) ER visits for migraines, 4) days of work lost due to migraines, 5) other costs directly related to migraines for 2 months. They will also be asked to

complete three questionnaires: the Migraine Work and Productivity Loss Questionnaire (MWPLQ),¹¹ the Migraine Disability Assessment questionnaire (MIDAS)¹² and the Migraine-Specific Quality of Life questionnaire (MSQ) at the time of enrollment.

All patients will undergo a history and physical examination, including an intranasal examination. This will include determination of the possible trigger site: frontal, temporal, occipital, and inferior turbinate/septum. The trigger site can be determined using a combination of three methods: 1) Physical examination, 2) Diagnostic botulinum toxin injection into a specific trigger point, and 3) Nerve block using a local anesthetic injected into a specific trigger point in patients having active symptoms.

The patients will be asked whether they prefer to undergo surgical decompression or a botulinum toxin protocol, and their preference will be recorded.

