50 patients who prefer surgery, and who satisfy the inclusion and exclusion criteria, will be included in the study as **Group A**. The location of the trigger site(s) will be determined based on history, physical examination, a diagnostic botulinum toxin injection and/or a nerve block. If those patients are found to have a trigger site that responds to botulinum injection, they will undergo surgical decompression of their trigger site, as described in Janis *et al*⁶ and Guyuron *et al*.⁷ Those patients will be followed postoperatively. They will be asked to continue tracking their 1) daily use of medications for migraines, 2) physician visits for migraines, 3) ER visits for migraines, 4) days of work lost due to migraines, and 5) other costs directly related to migraines for 2 months. At 1 year, 2 years and 2.5 years postoperatively, they will be asked to fill the Migraine Work and Productivity Loss Questionnaire (MWPLQ), the Migraine Disability Assessment questionnaire (MIDAS) and the Migraine-Specific Quality of Life questionnaire (MSQ) again. They will also be examined by a board-certified neurologist at 1 year postoperatively.

A separate sample of 50 patients from the pool of patients undergoing the botulinum toxin injection protocol will be selected (Group B). Those patients will be matched to the individual patients in group A based on gender, age (in 5 year intervals), migraine severity (based on the Migraine Disability Assessment questionnaire, 5 –point intervals) and trigger site (pair-matching). For example, for a patient in Group A who is a 47 year-old woman with temporal migraines and a MIDAS severity score of 14, a patient on the botulinum injection protocol will be included in Group B is she is a 45 to 50 year old female with temporal migraines and a MIDAS severity score of 10 to 15.

The patients in group B will receive the botulinum injection protocol, and will continue to track their 1) daily use of medications for migraines, 2) physician visits for migraines, 3) ER visits for migraines, 4) days of work lost due to migraines, and 5) other costs directly related to migraines for 2 months. At 1 year, 2 years and 2.5 years after the start of the protocol, they will be asked to fill the Migraine Work and Productivity Loss Questionnaire (MWPLQ), the Migraine Disability Assessment questionnaire (MIDAS)

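### Centre is neither a matching factor nor a model term, so the surgery-versus-botulinum comparison may be confounded by centre, and consistency between the two centres is not examined

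*SAP*

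**What the plan says.** **Matching.** Under Detailed study procedures (III.c), Group B patients are "matched to the individual patients in group A based on gender, age (in 5 year intervals), migraine severity" on the MIDAS, and trigger site. Data analysis (III.g) repeats the list: "based on gender, age, migraine severity and migraine location". Trigger site is anatomical, as the examination paragraph of III.c shows: "determination of the possible trigger site: frontal, temporal, occipital, and inferior turbinate/septum". It does not stand in for study centre.

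**Allocation.** Group A is made up of patients who prefer surgery (III.c). Group B is drawn from patients on the botulinum protocol. There is no randomisation, and no rule on centre.

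**Model.** The SAP specifies "Linear mixed models with a random effect for patient", used "to evaluate the changes in each of six outcomes between two different treatments over time". The fixed effects are treatment, time and their interaction. Centre appears only among the variables to be tabulated, in "treatment (Botox or Surgery) and site (OSU or MGH".

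**Aim.** The background section ends by stating the main aim: that the earlier results are "reproducible at other institutions and by other surgeons using similar techniques on different patient populations".

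**The concern.** Internal validity (III.e) claims that matched pairs remove confounding. That claim cannot extend to a factor left out of the matching. External validity (III.f) expects the centres to have different patients and different clinicians, so centre is a plausible source of difference in outcome. Because treatment follows preference, one centre could supply most of the surgery patients and the other most of the botulinum patients. Any difference between centres in improvement that remains after matching on the four listed factors would then be partly credited to treatment, in either direction.

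The second issue is interpretive. The background section says that most earlier results came from one institution and one author. With estimates pooled over both centres, a result found at both centres and a result driven by one of them would look the same in the report.

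**Working it through.** **1. Where centre could enter the plan**

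| Place | Factors used | Centre included? |
|---|---|---|
| Matching (III.c, III.g) | gender, age, MIDAS severity, trigger site | No |
| Within-group and paired t-tests (III.d, III.g) | group, time point | No |
| Mixed models (SAP) | treatment, time, interaction, patient | No |
| Descriptive tables (SAP) | sex, treatment, centre, age, outcomes | Yes, as counts only |

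**2. The plan's own figures.** The efficacy calculation in the sample-size section uses mean improvements in Migraine Headache Index (MHI) of 96.6% and 87.5%, a difference of 9.1 points, with SD 20%, alpha 5% and power 80%. Its 30 per group is reproduced as a one-sided paired calculation: (20 × (1.645 + 0.842) / 9.1)² = 29.9, rounded up to 30. A two-sided two-sample calculation gives 76. Centre plays no part in either. Below I use the 9.1 points, SD 20, the planned 50 per group and the SAP's two-sided 5% level. I treat the groups as independent, because the SAP model has no pair term.

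**3. Bias.** Let pA and pB be the shares of Groups A and B from one centre, and D the difference between centres in improvement. Then

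bias = (pA − pB) × D.

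The same formula applies to the protocol's paired t-test, since with complete pairs the mean within-pair difference equals the difference in group means. The documents give no shares and no D, so all values of both are assumptions.

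| Centre mix, A vs B | D = 5 | D = 10 |
|---|---|---|
| equal | 0 | 0 |
| 60/40 vs 40/60 | 0.2 × 5 = 1 (1/9.1 = 11%) | 0.2 × 10 = 2 (22%) |
| 70/30 vs 30/70 | 0.4 × 5 = 2 (22%) | 0.4 × 10 = 4 (44%) |

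**4. Effect on the error rate.** SE = 20 × √(2/50) = 4.0. With no true treatment effect, the chance of a significant result is Φ(bias/4 − 1.96) + Φ(−bias/4 − 1.96). A bias of 1 point gives 5.7%, 2 points gives 7.9%, and 4 points gives 17.0%, against a nominal 5%.

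**5. Precision cost of adjusting.** With equal groups and an overall 50/50 split by centre, the correlation between treatment and centre is φ = pA − pB, and the variance is inflated by 1/(1 − φ²). Power for 9.1 points is about Φ(9.1/SE − 1.96).

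| Mix | Inflation | SE | Power |
|---|---|---|---|
| equal | 1.00 | 4.00 | 62% |
| 60/40 vs 40/60 | 1.04 | 4.08 | 61% |
| 70/30 vs 30/70 | 1.19 | 4.36 | 55% |

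**6. Can consistency be tested formally?** With 25 patients per group at each centre, the SE of the treatment-by-centre interaction is 20 × √(2/25 + 2/25) = 8.0. Power for a 9.1-point interaction is about 21%, and the difference detectable with 80% power is 8.0 × 2.80 = 22.4 points. A formal test would tell the reader little.

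**The case against.** **Centre differences need not bias the comparison.** A reader might infer that every difference between centres passes into the treatment effect. The documents do not support that. Bias needs both a different centre mix in the two groups and a centre difference in change. No mix is reported, and an equal mix gives zero. Differences in gender, age, MIDAS severity and trigger site are addressed by the matching, although the SAP model carries neither the pairs nor these covariates. Stable differences in level also cancel from the treatment-by-time interaction, which carries the comparison of change. This objection stands and is why the point is stated conditionally.

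**The aim is not left untested.** A reader might also infer that reproducibility is never examined. Both centres differ from the institution of the earlier sham-controlled trial, so the pooled change in Group A does bear on whether its results recur elsewhere. Consistency between the two new centres is narrower, and the Objectives section does not list it. This also stands.

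**The size is assumed.** More extreme inputs can make the bias look nearly as large as the planned effect: 90% versus 10% with D = 10 gives 8 points, or 88% of 9.1. Nothing in the documents points to such a mix. All these figures are in MHI percentage points, while the SAP models ln(outcome + 1), so they show scale and do not predict the bias in the planned estimates.

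**Adjustment is not free.** Its cost is greatest where imbalance is greatest, as step 5 shows.

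None of this removes the omission. The plan neither prevents nor reports a difference in centre mix, and it has no means of adjusting for one.

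**Conclusion.** The point holds as a risk of confounding, not as demonstrated bias. It is certain that centre is absent from both the matching and the models, and that preference-based allocation leaves the centre mix uncontrolled. The size cannot be known from the documents. Under moderate assumed imbalance it is 1 to 4 MHI points, or 11% to 44% of the planning difference. At 70/30 versus 30/70 the two-sided error rises to about 8% to 17%. These figures assume SD 20 per patient, 50 per group, independent groups and a centre difference of 5 to 10 points that remains after matching.

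On reproducibility, the gap is the lack of any centre-specific result. The documents do not give the number of surgeons or injectors at each centre, so surgeon and centre effects may not be separable, and no claim about individual surgeons can be made from centre alone.

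**What to change.** In the SAP:

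1. Tabulate treatment by centre, so that a reader can see whether the condition for bias is met.
2. Add centre and centre-by-time as fixed effects in all six models. The second term is needed because the comparison is of change over time, and a centre main effect alone would leave a centre difference in change in place. With two centres, fixed effects are more suitable than random ones.
3. Report the surgery-minus-botulinum difference in change from baseline for OSU and MGH separately, with confidence intervals. This needs a supplementary model with a treatment-by-centre-by-time term, or separate fits by centre, because the terms in item 2 do not provide it. Label it descriptive and draw no conclusion from an interaction p-value.
4. State how many operators worked at each centre.

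If any pairs remain to be formed, prefer a same-centre match where one exists. The SAP is written in the past tense, so this may no longer apply.

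No new centre data are needed, since centre is already recorded. The cost is precision: on the figures above, power for 9.1 points falls from 62% to about 61% at 60/40 and 55% at 70/30, and further with greater imbalance. Centre-specific intervals will be wide.
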